# Suspected Unexpected Serious Adverse Reaction (SUSAR)

A serious adverse reaction, the nature and severity of which is not consistent with the information about the medicinal product in question set out:

- in the case of a product with a marketing authorisation, in the summary of product characteristics (SmPC) for that product
- in the case of any other investigational medicinal product, in the investigator's brochure (IB) relating to the trial in question.

NB: to avoid confusion or misunderstanding of the difference between the terms "serious" and "severe", the following note of clarification is provided: "Severe" is often used to describe intensity of a specific event, which may be of relatively minor medical significance. "Seriousness" is the regulatory definition supplied above.

Any pregnancy occurring during the clinical trial and the outcome of the pregnancy should be recorded and followed up for congenital abnormality or birth defect, at which point it would fall within the definition of "serious".

The relationship of each adverse event to the trial medication must be determined by a medically qualified individual according to the following definitions:

**Unrelated** – Where an event is not considered to be related to the IMP / intervention

**Possibly Related** – although a relationship to the IMP / intervention cannot be completely ruled out, the nature of the event, the underlying disease, concomitant medication or temporal relationship make other explanations possible.

**Probably Related** – the temporal relationship and absence of a more likely explanation suggest the event could be related to the IMP / intervention

**Definitely Related** – the known effects of the IMP, its therapeutic class or based on challenge testing suggests that the IMP / intervention is the most likely cause.

# **Foreseeable Events**

A large proportion of patients in this study are likely to have life limiting diseases. Patients with malignant pleural effusions who have been hospitalized have a 30 day mortality of 15% (6) and those with pleural infection have a 20% 3 month mortality. In this study, therefore, using the conventional timelines for adverse event reporting is not appropriate.

Disease related expected SAEs include: re-admission, death, and disease progression as judged by the local PI (or delegated person if the PI is unavailable). These will be recorded on the CRFs as expected adverse events but not subject to the timelines for SAE reporting.

Drain related expected AEs include: pain, infection, bleeding, organ puncture, hypoxia, persistent air leak, surgical emphysema, hypotension and prolonged length

of stay due to drain removal/displacement. All drain related adverse events as judged by the local PI (or delegated person if the PI is unavailable) will be captured on the CRFs up to 30 days after initial drain removal. At the 30 day telephone / clinical follow up point, CRFs will be used to record any further defined adverse events. Only those which are directly attributable to drain insertion / use / removal will be recorded at this point.

Unexpected adverse events are those not on the list above that in the investigators view is directly attributable to the chest drain. If these are serious (i.e. Serious and Unexpected Adverse Event), these events will be subject to expedited reporting to the sponsor as per SUSAR guidelines.

# 12.2 RECORDING ADVERSE EVENTS (AES)

All drain related Adverse Events will be recorded in the hospital notes and Case Report Form (CRF). Only AEs felt to be directly attributable to the chest drain should be recorded. All expected AEs will be collected on the CRFs so separate AE forms do not need to be completed. Unexpected AEs will be reported in the normal manner.

If the Investigator suspects that the disease has progressed faster due to the administration of the study treatment/procedure, then he/she will report this as an unexpected adverse event to Oxford Respiratory Trials Unit who will refer to the Sponsor and the main REC, if appropriate, as detailed in Section 12.3.

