### 12.3 REPORTING SAES

Only related, unexpected SAEs occurring as judged by the local PI (or delegated person if the PI is unavailable) will be reported up to 30 days after initial drain removal. These should be reported on the ORTU reporting form to ORTU within 24 hours of the Site Study Team becoming aware of the event at [contact] ORTU will perform an initial check of the report, and ensure the SAE is reviewed by the Medical Reviewer (including expectedness assessment), if appropriate the sponsor and the main REC will also be notified. The SAE will also be reviewed at the next ORTU Safety Oversight Group meeting. Additional and further requested information (follow-up or corrections to the original case) will be detailed on a new SAE Report Form and reported to ORTU.

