# 14.2.2 Secondary endpoints

- 1. To assess the difference in patient reported pain scores, using a visual analogue scale.
- assessed by simple measurement of the distance of the line drawn by the patient from the left hand end of the VAS.2. To assess the frequency complications such as balloon rupture, drain blockage or other drain related complications
  - Assess balloon rupture in the interventional arm only, by inflation of the balloon with fluid after removal (accidental or intentional) from the pleural space.
  - Assessed by review of medical notes or patient review whilst the original chest drain is in situ
- 3. To assess the difference in the length of hospital stay
  - Record the number of days, after insertion of the initial study drain, that the patient was discharged (Including day of drain insertion and date of discharge)
- 4. To assess the total number of pleural procedures (including surgical procedures) in the 30 days after the initial study drain was removed
  - Record the number of pleural procedures undertaken in the 30 days after the initial study drain was removed
- 5. To assess the number of days which the patient has any chest drain in situ in the 30 days after the initial drain removal
  - Record the number of days the patient had a chest drain in situ in the 30 days after the initial study drain was removed after the initial study drain was removed
- 6. To record the total number of radiological investigations performed from the time of drain insertion until the 30 day follow up has been completed
  - Assessed by review of medical notes radiology systems.
- 7. To record the consequences of drain displacement such as failed treatment, delayed discharge the need for subsequent pleural procedures or the need for further medical or surgical care
  - Assessed by review of medical notes and/or patient review.

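### Adverse events are filtered by the local investigator's attribution with the arm known, which risks uneven capture between arms, and Sections 12.1 and 12.2 conflict on recording disease-related deaths and re-admissions

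*Protocol*

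**What the plan says.** **Recording rule.** Section 12.2: "Only AEs felt to be directly attributable to the chest drain should be recorded". For the 30-day telephone or clinic follow-up, Section 12.1 (Foreseeable Events) adds: "Only those which are directly attributable to drain insertion / use / removal will be recorded at this point". The same part of Section 12.1 gives the judgement of drain-relatedness to the local PI or a delegate.

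**Disease-related events.** Section 12.1: "Disease related expected SAEs include: re-admission, death, and disease progression as judged by the local PI". It then says of these: "These will be recorded on the CRFs as expected adverse events but not subject to the timelines for SAE reporting". In Section 12.2, the sentence straight after the attribution rule reads: "All expected AEs will be collected on the CRFs so separate AE forms do not need to be completed".

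**Endpoint.** Secondary endpoint 2 in Section 14.2.2 is: "To assess the frequency complications such as balloon rupture, drain blockage or other drain related complications". It is assessed by notes or patient review while the original drain is in place. Balloon rupture is tested in the interventional arm only.

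**Other routes.** Section 10.4 lists complications among the data collected while the drain is in situ, at discharge and at 30 days, with no attribution condition. The causality scale in Section 12.1 is to be applied to each adverse event and has an unrelated grade.

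**The concern.** Relatedness is normally recorded about an event that has already been captured. Here it decides whether the event is captured at all. Several events on the protocol's own drain-related list (infection, hypoxia, hypotension, bleeding, persistent air leak) can come from the drain or from the pleural disease that led to enrolment. An investigator who knows the arm may attribute such events more readily, or less readily, to a new balloon device than to a familiar drain. If so, the recorded complication rates would differ between arms even where the true rates do not. Events never written down cannot be recovered by any analysis plan.

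The second matter is one of consistency. A site that follows the attribution sentence in Section 12.2 would leave out a disease-related death or re-admission. A site that follows Section 12.1 would record it. All-cause deaths and re-admissions could therefore be incomplete, and incomplete in different ways at different sites.

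**Working it through.** **1. Who decides on attribution, and is the arm known?** Section 12.1 names the local PI or delegate. The protocol describes no blinding. Section 11.3.1 describes a drain that differs visibly, with a balloon and a separate inflation channel. That the local PI or delegate knows the arm is an inference, but a safe one.

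**2. Is there an independent check on relatedness?** Section 12.3 restricts SAE reports: "Only related, unexpected SAEs occurring as judged by the local PI". The Medical Reviewer therefore sees only events that the site has already called related. The review content named there is expectedness, and Appendix 3 places the relatedness assessment on the form the PI completes. Ordinary AEs have no independent check.

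**3. The instructions side by side.**

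| Place | What is to be recorded |
|---|---|
| 10.4 | Complications in situ, at discharge and at 30 days; no attribution condition |
| 12.1, causality scale | Each AE graded, unrelated included |
| 12.1, Foreseeable Events | Disease-related re-admission, death and progression go on the CRF |
| 12.1, 30-day rule | Drain-attributable events only |
| 12.2, attribution sentence | Drain-attributable AEs only |
| 12.2, next sentence | All expected AEs |

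Disease-related deaths are expected events under 12.1, so the two sentences in 12.2 give opposite answers for them. Under the attribution sentence the unrelated grade would never be used. The 30-day items listed in 10.4 (complications, final diagnosis, further pleural interventions, days with a drain) do not name death or re-admission.

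**4. How many deaths could the conflict touch?** Section 12.1 gives 15% 30-day mortality for hospitalised malignant effusion, and Section 14.1 gives 267 patients. The share with malignant effusion is not given. Assuming 25% to 100%: 267 × 0.25 × 0.15 = 10 and 267 × 1.00 × 0.15 = 40. So about 10 to 40 deaths.

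**5. What could unequal attribution do?** The protocol states no figure for this, so there is none to reproduce. For the arm size I use its own formula in Section 14.1 with 12% v 3%: n = (1.960 + 0.842)² × (0.12 × 0.88 + 0.03 × 0.97) / 0.09² = 130.5, so 131 per arm.

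Recorded rate = true rate × probability of attribution. The true rate is the same in both arms. The probability of two-sided p < 0.05 comes from the normal approximation for two proportions. True rates and attribution probabilities are **assumed**.

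Worked case, true rate 15%, attribution 70% v 90%:
- recorded rates 0.15 × 0.70 = 10.5% and 0.15 × 0.90 = 13.5%; ratio 1.29
- standard error √[(0.105 × 0.895 + 0.135 × 0.865)/131] = 0.0401
- difference / standard error = 0.030/0.0401 = 0.75
- probability of significance about 12%

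| True rate, both arms | Equal attribution | 70% v 90% | 60% v 90% |
|---|---|---|---|
| 2% | 5% | 6% | 7% |
| 5% | 5% | 7% | 10% |
| 10% | 5% | 9% | 15% |
| 15% | 5% | 12% | 21% |
| 30% | 5% | 21% | about 42% |

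The recorded ratio is 1.00, 1.29 and 1.50 in the three attribution columns, whatever the true rate, and it could run in either direction.

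**The case against.** The strongest reply is that Section 12 is not the only route to the endpoint. Section 10.4 collects complications without asking about cause. The assessment charts schedule them at insertion, during days 0 to 5 and at removal. Section 14.2.2 has its own notes or patient review in both arms. This stands: a reader might infer that no complication reaches the CRF unless attributed to the drain, and the documents do not support that. It does not remove the problem. Section 14.2.2 still limits the endpoint to drain-related complications, its review covers only the time the original drain is in place, and Section 12.1 restricts the 30-day record that Section 10.4 leaves open.

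A reader might also infer that the two arms cannot be compared without bias. That is not supported either. Bias needs attribution to differ by arm, nothing in the protocol shows that it does, and for uncommon complications the effect is small (6% to 10% at true rates of 2% to 5%).

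On deaths, it can be said that Section 12.1 is explicit, that the second sentence of Section 12.2 agrees with it, and that the notes review in Sections 10.4 and 13.3 would probably bring deaths to light. This makes complete recording more likely but leaves contradictory instructions in place.

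The frailty of the population, which Section 12.1 cites, is a sound reason for not using conventional reporting timelines. It is not a reason to leave occurrences off the CRF.

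Finally, restricting an endpoint to drain-related complications is a legitimate choice. Counting every infection or air leak would bring in the presenting disease. That stands, and it limits the remedy.

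**Conclusion.** The point holds as a risk of differential ascertainment together with a set of inconsistent instructions. As written, Section 12.2 and the 30-day rule make a judgement by someone who knows the arm a filter on AE recording. They do not fit with Section 10.4 or with the causality scale. The size of any resulting bias is unknown: zero if attribution is equal in both arms, and about 12% false positives instead of 5% under the assumed 15% rate with 70% v 90% attribution.

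The conflict over disease-related deaths, re-admissions and progression, between Sections 12.1 and 12.2 and within 12.2, is plain from the text and needs no assumption. A reader might infer that it also distorts the complication comparison. It does not, because those events are not part of secondary endpoint 2. What it puts at risk is the completeness of all-cause safety data to 30 days.

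This should be corrected in the protocol, since an analysis plan cannot supply events that were never collected.

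**What to change.** 1. Delete or reword the two sentences that restrict recording to attributable events (Section 12.2 and the 30-day rule in Section 12.1), so that Sections 10.4, 12.1 and 12.2 agree.
2. Record all deaths and re-admissions to 30 days after drain removal in both arms, with explicit CRF fields.
3. Record in both arms, whatever the attribution, every new or worsening occurrence after drain insertion of the drain-related events listed in Section 12.1, plus the complications named in the objectives (blockage, surgical emphysema, nerve damage, intercostal injury; balloon rupture in the interventional arm). The new-or-worsening condition keeps the presenting infection or air leak from being counted as such.
4. Make relatedness a separate CRF field, so that the existing causality scale can be used.
5. Keep drain-related complications as secondary endpoint 2, and report all occurrences by arm alongside as a sensitivity comparison.

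Expedited reporting stays as it is. The cost is a few more fields on CRFs that are already completed with notes review, and some disease-related background events in the all-occurrence counts. For infection and air leak that background could be substantial, which is why the all-occurrence count should not become the main analysis.

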### 12.3 REPORTING SAES

Only related, unexpected SAEs occurring as judged by the local PI (or delegated person if the PI is unavailable) will be reported up to 30 days after initial drain removal. These should be reported on the ORTU reporting form to ORTU within 24 hours of the Site Study Team becoming aware of the event at [contact] ORTU will perform an initial check of the report, and ensure the SAE is reviewed by the Medical Reviewer (including expectedness assessment), if appropriate the sponsor and the main REC will also be notified. The SAE will also be reviewed at the next ORTU Safety Oversight Group meeting. Additional and further requested information (follow-up or corrections to the original case) will be detailed on a new SAE Report Form and reported to ORTU.

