# **15.2 Safety Oversight Group**

The Oxford Respiratory Trials Unit (ORTU) Safety Oversight Group will conduct a review of all SAEs for the trial reported during the reporting period and cumulatively. The ORTU Safety Oversight Group requires at least three clinicians to attend each meeting (this may include the Chief Investigator). The Group will provide advice to the TSC and may correspond directly with the Sponsor if potential safety concerns are raised. The aims of this committee include:

- To pick up any trends, such as increases in un/expected events, and take appropriate action
- To seek additional advice or information from investigators where required
- To evaluate the risk of the trial continuing and take appropriate action where necessary

The content and timings of the ORTU Safety Oversight Group will be detailed in a Safety Oversight Group Charter, which will be agreed with the members.

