# **Appendix 2: Study Drain Design Diagrams**

**Appendix 3: ORTU Safety Reporting Process** 

#### ORTU safety reporting process - overview Serious Adverse Event V1.0 Jan 2019 ORTU SAE form completed by PI including Relatedness Assessment Medical Reviewer: Clinician with Completed SAE form sent to knowledge of the speciality that is not ORTU ([contact]) linked (not PI or within 24 hours of site recruiting for the becoming aware trial) to the specific trial. ORTU has a pool of medical reviewers with SAE logged by Trial Manager reviewers being Safety Oversight (TM) and sent to Medical specified for each Group: The ORTU trial. At least one Reviewer or delegate has a Safety medical reviewer. Oversight Group to immediately plus a back up, for provide periodic each trial. oversight of all SAE reported in ORTU ORTU Medical Review Form studies. Quorum If SUSAR or Related requires at least 3 Unexpected SAE. completed by Medical clinicians in trigger expedited attendancewho Reviewer including reportingto review aggregate appropriate oversight Expectedness Assessment data. bodies Medical Reviewer submits ORTU Medical Review form to TM for a QC check and for logging. TM to provide line listings (and other details) as required to Safety Oversight Group to review aggregate SAE data

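### The Safety Oversight Group must watch for rises in expected events, but serious drain-related events on the expected list have no stated route to it

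*Protocol*

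**What the plan says.** Five parts of the protocol bear on this.

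- **Section 12.1, Foreseeable Events.** The list of expected drain-related events opens: "Drain related expected AEs include: pain, infection, bleeding, organ puncture, hypoxia, persistent air leak, surgical emphysema, hypotension". Its last entry is a longer admission caused by loss or removal of the drain. What is unexpected is then defined by exclusion: "Unexpected adverse events are those not on the list above that in the investigators view is directly attributable to the chest drain". Death, re-admission and disease progression are classed separately as expected disease-related SAEs. They are recorded on the CRF and exempted from the SAE reporting timelines.
- **Section 12.2.** "All expected AEs will be collected on the CRFs so separate AE forms do not need to be completed".
- **Section 12.3.** "Only related, unexpected SAEs occurring as judged by the local PI (or delegated person if the PI is unavailable) will be reported". The reporting window closes 30 days after removal of the initial drain, and each report is due within 24 hours of the site becoming aware. For an event so reported: "The SAE will also be reviewed at the next ORTU Safety Oversight Group meeting". The same section places the expectedness assessment with the Medical Reviewer.
- **Section 15.2.** The Group reviews the trial's reported SAEs, both for the period and cumulatively. Its first listed aim is "To pick up any trends, such as increases in un/expected events, and take appropriate action".
- **Appendix 3.** The PI completes the SAE form with a relatedness assessment. A Medical Reviewer not linked to the trial then assesses expectedness. The trial manager gives the Group line listings, and other details as required, so that it can "review aggregate SAE data".

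**The concern.** The Group is given an aim for which the protocol names no data. It is to notice a rise in expected events, but its described input is the set of reported SAEs, and the reporting rule removes expected events before they enter that set.

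The events removed are not trivial. Organ puncture, bleeding and infection can be serious harms of placing and keeping a drain. Section 4.4 names incorrect positioning at the time of balloon inflation as a remaining risk; it is a reasonable inference, though not stated, that this could show itself as bleeding or organ puncture. The prior experience cited for the device in section 4.3 is a pilot of 20 patients. Section 7.3 allows early termination for an apparent safety issue with the interventional drain, so it matters whether a difference between arms in serious listed events could become apparent while the trial is running.

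There is a second weakness. If the local PI decides that a serious event is expected, no report is made, and the Medical Reviewer never has the chance to disagree.

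**Working it through.** **1. Following one event through the text.** Take a serious organ puncture attributed to the drain, in either arm.

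| Step | Rule | Result |
|---|---|---|
| Is it on the expected list? | 12.1, Foreseeable Events | Yes; the list sets no seriousness limit |
| Is it unexpected? | 12.1: unexpected means not on the list | No |
| Where is it recorded? | 12.2 | On the CRF |
| Is it reported as an SAE? | 12.3: related and unexpected only | No |
| Does the Medical Reviewer see it? | 12.3, Appendix 3: reviews submitted SAE forms | No form, so no |
| Is it in what the Group reviews? | 15.2: reported SAEs; Appendix 3: SAE listings | Not by any stated route |
| Is it within the Group's aim? | 15.2: increases in expected or unexpected events | Yes |

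The last two rows conflict. Deaths and re-admissions classed as disease-related end the same way: on the CRF, with no stated feed to the Group.

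**2. Who decides expectedness.** Appendix 3 runs in this order: the PI judges relatedness, the form is sent, the Medical Reviewer judges expectedness, and expedited reporting follows if the event is related and unexpected. That final condition has work to do only if some submitted SAEs turn out to be expected. Section 12.3 has already excluded those at the site, so the central step can overturn a site's call of unexpected but never a call of expected.

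**3. Scale, for illustration only.** The protocol states no rate for serious listed events, so the rates below are assumptions.

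Arm size: section 14.1 gives a revised total of 267. Its formula for 12% versus 3%, taking the originally stated 5% significance level (two-sided) and 80% power as unchanged, gives

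n = (1.960 + 0.842)² × (0.12 × 0.88 + 0.03 × 0.97) / 0.09² = 130.5, rounded up to 131 per arm.

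Then 2 × 131 / 0.98 = 267.3, which agrees with 267. Half of 267 is about 133 per arm.

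With assumed rate p in one arm, the expected count is 133p and the chance of at least one event is 1 − (1 − p)^133:

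| Assumed p | Expected events | Chance of at least one |
|---|---|---|
| 1% | 1.3 | 74% |
| 2% | 2.7 | 93% |
| 5% | 6.7 | 99.9% |

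Under section 12.3 as written, none of these would be reported as an SAE.

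For a contrast between arms, assume 3% with the balloon and 1% with the standard drain, 131 evaluable patients each: 131 × 0.03 = 3.9 and 131 × 0.01 = 1.3, or about 4 against 1. Conditional on 5 events in equal arms, the exact two-sided p-value is 2 × (5 + 1)/2⁵ = 12/32 = 0.375. Counts of this size would not establish an excess. Their use would be to prompt clinical review of the individual events and of any trend.

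**The case against.** A reader might infer that these events can never reach the Group. The documents do not support that. Appendix 3 lets the trial manager supply further details as required, section 15.2 lets the Group seek information from investigators, and its content and timings are left to a Charter that is not shown. The data sit on CRFs in a central web-based system (section 13.2) and can be retrieved. This stands: the gap is the absence of a stated route. Against it, information available on request is not a regular feed, and a Charter entry would not remove the restriction in 12.3 or the site's filter on expectedness.

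A reader might also infer that the Group is the trial's only ongoing safety check, so that an excess would stay hidden until final analysis. Section 15.1 gives the Trial Management Group a duty to monitor the trial and safeguard participants, and section 14.1 shows the TSC looking at accumulating data at half recruitment. That TSC review concerned the displacement rate, and no safety data feed to the Trial Management Group is described, but the stronger statement still fails.

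Nor is the gap specific to the balloon. The list applies to any drain. Tissue necrosis and balloon rupture are not on it, so if serious and judged related they are reported and do reach the Group.

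It can be argued that an unusually severe listed event might count as unexpected: the SUSAR definition in 12.1 refers to nature and severity, and the drain list speaks of AEs where the disease list speaks of SAEs. The wording is not free of ambiguity. The operative definition for this trial, however, is absence from the list, and that has no severity term.

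Finally, section 12.1 gives a sound reason for limiting reporting, namely high background mortality, and section 4.4 notes that the device is CE marked. Both support relaxed timelines. Neither explains an oversight aim without matching data.

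**Conclusion.** The conflict is in the text and does not depend on any figure. Sections 12.1 to 12.3 remove serious listed drain-related events from SAE reporting, while section 15.2 asks the Group to detect increases in expected events from reported SAEs. The site filter also pre-empts the expectedness assessment that section 12.3 and Appendix 3 assign to the Medical Reviewer.

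The conclusion is limited to this: such events, in either arm, have no stated route to the Group, and a difference between arms may therefore not be visible to it during the trial. It rests on reading expectedness from the list, as Foreseeable Events directs, and on no other document adding a feed; the Charter could. How many events are affected is unknown, and the counts above rest on assumed rates.

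This should be fixed but is not critical. The sample size and the analysis of the primary endpoint are unaffected, and the events are captured on the CRF.

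**What to change.** Reconcile sections 12.1 to 12.3 with section 15.2 and Appendix 3.

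1. State in 12.3 and 15.2 that, before each Group meeting, the trial manager supplies CRF-derived counts by arm of all serious drain-related events regardless of expectedness, plus deaths and re-admissions.
2. Withhold by-arm data from any member who recruits to the trial, including the Chief Investigator. Section 15.2 allows the Chief Investigator to attend, section 8 allows that person to screen and consent patients, and the primary endpoint rests partly on local judgement.
3. Have sites report related SAEs without filtering on expectedness, and have the Medical Reviewer assign it, as Appendix 3 describes.
4. State which reports the existing 24-hour and expedited timelines cover. The 24-hour limit in 12.3 currently applies to every SAE reported, so removing the site filter would otherwise widen it unintentionally.

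The cost is one periodic table from data already collected, a few more SAE forms, and a closed session for the by-arm data.
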